## 9.2 Data Quality Assurance

The Sponsor or Sponsor's designee will conduct a site visit or a site phone contact, in case the investigator and the center are already known from DBV, to verify the qualifications of each Investigator, inspect the site facilities, inform the Investigator of his/her responsibilities and the required procedures for ensuring adequate site selection and proper documentation.

## 9.3 Database Management and Quality Control

All data generated by the site personnel will be captured electronically at each study center using e-CRFs. Data from external sources (such as laboratory data and exploratory BAT) will be imported into the central database.

Once clinical data are entered and validated in the e-CRF, they are transmitted and recorded by the central server in the central database. Computerized edit-checks will be developed in addition to manual review to detect any discrepancies and to ensure consistency of the data. The appropriate staff at the study site will answer queries sent to the Investigator. The reason for changes, the name of the person who performed the changes, together with the time and date will be automatically record by the Electronic Data Capture (EDC). An electronic audit trail system will be used to track all data changes in the database subsequent to the first data entry

If additional corrections are needed, the responsible monitor or data manager or the Sponsor will raise a query in the EDC application. Appropriate feedback to the study staff or other corrective measures will be undertaken if any missing data, inconsistent data, outlier data and potential protocol deviations are identified during routine remote data review.

Once all source data verification is complete and all queries are closed, the monitor will freeze the e-CRF page.

The specific procedures to be used for data entry and query resolution using the EDC system/e-CRF will be provided to study sites in a training manual. In addition, site personnel will receive training on the EDC system/e-CRF.

## 9.4 Source Documentation

All source documents from which e-CRF entries are derived should be kept in the subject's medical records.

For all e-CRF entries, for each subject, it must be possible to check these against source documents at the study site, excepted for the data generated for the study and recorded directly in the e-CRF.

As a minimum requirement, the following data must be source data verifiable in the subject's source documentation other than the e-CRF:

- Identification of subject (subject identifier: subject name, sex and date of birth)
- Confirmation of participation in the study (study identification, subject identification number and signed and dated informed consent);
- Diagnosis/indication under investigation;
- Relevant medical history, concomitant illness;
- Visit dates;
- Data related to the adverse events;
- Reason for subject exclusion during the selection or withdrawal from the study;

The Investigator will receive the laboratory reports from the central laboratory. The Investigator must review, sign and date the laboratory reports on the day of evaluation. The signed laboratory reports must be retained by the site as source documentation.

Data that will be entered directly into the e-CRF (those for which there is no prior written or electronic record of data) are considered to be source data. These data will be defined in the monitoring guidelines.

The pre-specified e-CRF entries, depending on the pre-specified source verified data, for each subject should be checked against source documents at the study site by the site monitor. Instances of missing or uninterpretable data will be discussed with the Investigator for resolution.

#### **9.5 Data Collection/ electronic Case Report Form (e-CRF)**

The Investigators (and appropriately authorized staff) will be given access to an online web-based EDC/e-CRF system, which is Food and Drug Administration (FDA) 21 CFR Part 11 compliant. This system is specifically designed for the collection of the clinical data in electronic format. Access and rights to the EDC system will be controlled and configured according to each individual's role throughout the study. In general, only the Investigator and authorized staff will be able to enter data and make corrections in the e-CRFs.

The specific procedures to be used for data entry and query resolution using the e-CRF will be provided to study sites in a training manual. In addition, site personnel will be trained on the e-CRF system.

The e-CRF should be promptly completed for each subject form whom an ICF was obtained and should reflect the latest observations on the subject participating in the study. Therefore, the e-CRFs are to be completed as soon as possible during or immediately after the subject's visit or assessment. The Investigator must verify that all data entries in the e-CRF are accurate and correct. If some assessments cannot be done, or if certain information is unavailable, not applicable or unknown, the Investigator should indicate it in the e-CRF.

Computerized data-check programs and manual checks will identify any clinical data discrepancies for resolution. Corresponding queries will be loaded into the system and the site will be informed about new issues to be resolved on-line. All discrepancies will be solved on-line directly by the Investigator or by authorized staff. Off-line edit checks will be done to examine relationships over time and across panels to facilitate quality data.

Information concerning IMP dispensation to the subject will be tracked in the e-CRF. After completion, the Investigator will be required to validate and electronically sign-off the clinical data recorded in each e-CRF.

## 9.6 Access to Source Data

### 9.6.1 Routine Monitoring

During the study, a Contract Research Organization (CRO) site monitor will make site visits to review protocol compliance, compare e-CRF entries and individual subject's medical records, assess drug accountability, and ensure that the study is being conducted according to ethical and pertinent regulatory requirements. The e-CRF entries will be verified with source documentation. The review of medical records will be performed in a manner to ensure that subject confidentiality is maintained.

Checking of the e-CRF entries for completeness and clarity, and cross-checking with source documents, will be required to monitor the progress of the study. Direct access to source data will be required for the monitoring activities.

### 9.6.2 Inspections and Auditing Procedures

The Sponsor or its representative may conduct audits at the investigative sites including, but not limited to, drug supply, presence of required documents, the informed consent process, and comparison of e-CRFs with source documents. All medical records (progress notes) must be available for audit. The Investigator agrees to participate in audits conducted at a convenient time in a reasonable manner.

Moreover, Regulatory Authorities of certain countries, IRBs and IECs may wish to carry out such source data checks and/or on-site audit inspections. Direct access to source data will be required for these inspections and audits; they will be carried out giving due consideration to data protection and medical confidentiality. The Investigator assures CRO and the Sponsor of the necessary support at all times.

The purpose of an audit is to assess whether ethics, regulatory and quality requirements are fulfilled.

## 9.7 Data Processing

All data will be entered by site personnel into the e-CRF (as detailed in Section 9.3).

The data-review and data-handling document, to be developed during the initiation phase of the study, will include specifications for computerized edit-checks: consistency and plausibility checks on data and will also include data-handling rules for obvious data errors. Query/correction for unresolved queries will be automatically sent for resolution with the Investigator. The database will be automatically updated after corrections are made by the investigator's staff.

Previous and concomitant medications will be coded using the WHO Drug Reference List, which employs the Anatomical Therapeutic Chemical (ATC) classification system. Disease and Medical histories/current medical conditions and AEs will be coded using the MedDRA terminology.

The actual versions of the coding dictionaries will be provided in the CSR.

### 9.8 Archiving Study Records

All data derived from the study will remain the property of the Sponsor. Records must be retained in accordance with the current ICH Guidelines on GCP. All essential study documents including records of subjects, source documents, e-CRFs and IMP inventory must be kept in a study-specific file.

Trial documents should be retained until at least 2 years after the last approval of a marketing application in an ICH region and until there are no pending or planned marketing applications in an ICH region or at least 2 years have elapsed since the formal discontinuation of clinical development of the product.

For this study, the Investigator site files records must be retained by the Investigator at least 15 years after the completion of the trial, or longer if required by their national regulation.

Subjects' medical records must be kept for the maximum period permitted by the hospital, institution or private practice.

The Investigator will not discard any relevant records to this study without prior written permission from the Sponsor. The Investigator shall notify the Sponsor in writing of their intent to destroy all such material. The Sponsor shall have 30 days to respond to the Investigator's notice, and the Sponsor shall have a further opportunity to retain such materials at the Sponsor's expense.

The Investigator shall take responsibility for maintaining adequate and accurate hard copy source documents of all observations and data generated during this study. Such documentation is subject to inspection by the Sponsor, its representatives and Regulatory Authorities. If an Investigator moves, withdraws from the study or retires, the responsibility for maintaining the records may be transferred to another person who will accept responsibility. Notice of transfer must be made to and agreed by the Sponsor.

### 9.9 Good Clinical Practice

The procedures set out in this study protocol are designed to ensure that the Sponsor and Investigator abide by the principles of the ICH-GCP Guidelines, and of the Declaration of Helsinki (APPENDIX 1). The study also will be carried out in keeping with local legal requirements.

### 9.10 Protocol Approval and Amendment

Before the start of the study, the study protocol and/or other relevant documents will be reviewed and approved by the IEC/IRB/Regulatory Authorities, in accordance with local legal requirements. The Sponsor must ensure that all ethical and legal requirements have been met before the first subject is enrolled in the study.

This protocol is to be followed exactly. Any change to the protocol must be handled as a protocol amendment. Any potential amendment must be approved by the Sponsor. A written amendment must be submitted to the appropriate Regulatory Authorities and to the IRB/IECs assuming this responsibility. The Investigator must await IRB/IEC approval of substantial protocol amendments before implementing the changes, except where necessary to eliminate apparent immediate hazard to subjects.

All substantial amendments to the protocol must be approved in writing by both the appropriate Regulatory Authorities and the IRB/IEC, except for administrative amendments, which require notification but not written approval. Once approved, the protocol amendment will be distributed to all recipients of the original protocol, with instructions to append the amendment to the protocol. If, in the judgment of the local IRB/IEC, the Investigator and/or Sponsor, the protocol amendment alters the study design, procedures and/or increases the potential risk to the subject, the currently approved written ICF will require modifications. The modified ICF must also be reviewed and approved by the Sponsor, appropriate Regulatory Authorities, and the IRB/IEC. In such cases, repeat informed consent must be obtained from the enrolled subjects' parents/guardians before participation continues.

### 9.11 Data and Safety Monitoring Board

A DSMB composed of experts in food allergy and in the methodology of clinical studies will be established in due time for the first data review. This DSMB will be independent of the Sponsor and will review safety data from the study at specified intervals during the study and on an ad hoc basis as deemed necessary by the DSMB Chair person or when conveyed by the Sponsor.

The DSMB members will review blinded data, but may have access to unblinded data as deemed necessary during the closed review meetings. During these review meetings, the DSMB will assess whether the nature, frequency, and severity of the AEs associated with the study treatment warrant any recommendations or corrective actions of the study conduct in the best interest of the subjects.

A specific DSMB meeting will review the safety analysis on the initial 50 first subjects included in the 3 treatment arms of the Part A, DBV712 100 µg and 250 µg and placebo when they will reach 3 months of patch application. These safety data will be reviewed unblindly by the DSMB for forming their recommendation on the dose selection for the study part B.

Another specific DSMB meeting will be conducted on the futility analysis based on peanut-specific IgG4 measurements and the safety data when all the subjects of the Part B will reach 6 months of treatment. These data will be reviewed unblindly by the DSMB for forming their recommendation on the continuation of the study.

The roles, responsibilities, constitution, and operations of the DSMB will be described in the DSMB Charter, which will be reviewed and signed by each member before the first subject is enrolled in the study.

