### Study Part B

The second part of the study aims to assess the safety and efficacy of the selected dose after 12-month treatment *versus* placebo. This part was to be initiated after the choice of the highest safe dose upon the DSMB meeting. As from protocol v6.0, the selected highest safe dose for part B upon DSMB recommendation is 250 µg. Additional subjects will be recruited in the active selected dose arm and in the placebo arm, to reach the targeted total number of subjects. In accordance with the calculated sample size for this study, a total of 350 additional subjects will be randomized in the second part (Part B) of the study. These subjects will be randomized with a 2:1 ratio in either the active or placebo arm, 233 subjects in the active arm and 117 subjects in the placebo arm.

An interim analysis to evidence the treatment activity on the immune system of 1 to 3 years old children is planned after the first 50 subjects from part B have received 6 months of active treatment with the selected DBV712 dose of 250 µg (Visit 8). This analysis, encompassing peanut-specific IgE, peanut-specific Immunoglobulin G4 subtype (IgG4), SPT and main safety data, will specifically be conducted on the measurements of the peanut-specific IgG4. The relative change from baseline of the peanut-specific IgG4 levels in the DBV712 250 µg

treatment group at Month 6 will be numerically compared to the relative change from baseline of the peanut-specific IgG4 levels in the placebo group at Month 6. The median relative change in IgG4 of the DBV712 250 µg treatment group is expected to be greater than the median relative change in IgG4 of the placebo treatment group.

In the situation where the median relative change from baseline of the peanut specific IgG4 is equal or lower than the median relative change in the placebo group, the premature stop of the study for lack of evidence of therapeutic benefit will be considered. This unblinded data review will be conducted by the DSMB who will be responsible of issuing the recommendation to the sponsor.

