#### Interim analyses

##### End of Part A safety analysis

A safety analysis was to be conducted on the initial first 50 subjects included in the 3 treatment arms, DBV712 100 µg, DBV712 250 µg and placebo after 3 months of patch application. These safety data was to be reviewed by the DSMB and their members were to release their recommendation on the safe dose to select for the study part B. Upon review of the 3-month safety data of the 51 randomized subjects in part A, the DSMB had no safety concern and considered both doses as well tolerated with a good safety profile. The 250-µg dose was selected for part B.

For the subjects in the Part A, depending on the DSMB recommendations, the dose of the 2 DBV712 groups were either to be kept unchanged or adjusted. The study could also be definitively discontinued. Upon DSMB recommendations, all subjects from Part A are to remain in their initially randomized treatment arm.

##### Interim futility analysis of the IgG4 immunological response at Month 6

This analysis will be conducted when 50 subjects from Part B have reached 6 months of active treatment with the active DBV712 dose selected in the Part A (250 µg). This analysis will be conducted more specifically on peanut specific IgG4 measurements. The median relative change from baseline of the peanut specific IgG4 levels in the selected active DBV712 treatment group (250 µg) will be compared to the median relative change from baseline of the peanut specific IgG4 levels in the placebo group. The median value of the selected active group (250 µg) is expected to be greater than the median value of the placebo group.

[figure not shown]
In the situation where the change from baseline of the peanut specific IgG4 is equal to or lower than the change in the placebo group, the premature stop of the study for lack of evidence of treatment activity will be considered. This unblinded data review will be

conducted by the DSMB who will be responsible of issuing the recommendation to the Sponsor.

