##### 3.3.1.3 Other Efficacy Endpoints

- The percentage of subjects reaching a cumulative dose  $\geq 1,444$  mg peanut protein at the post treatment DBPCFC at Month 12 in the selected active DBV712 group (250 µg) *versus* the placebo group;
- The percentage of subjects reaching a cumulative dose  $\geq 3,444$  mg peanut protein at the post-treatment DBPCFC at Month 12 in the selected active DBV712 group (250 µg) *versus* the placebo group;
- The percentage of subjects unresponsive (those showing no symptoms leading to DBPCFC stop) to the highest dose of peanut protein (2,000 mg of peanut protein) in the selected active DBV712 group (250 µg) *versus* the placebo group.
- The change from baseline in peanut-specific IgE and IgG4 at months 3, 6 and 12 in the selected active DBV712 group (250 µg) *versus* the placebo group;
- The change from baseline in peanut-specific IgG4 at month 6 in the selected active DBV712 group (250 µg) *versus* the placebo group will be the main criteria of the interim 6-month analysis of the first 50 subjects treated with the selected dose of DBV712;
- The change from baseline in peanut SPT average wheal diameters at months 3, 6 and 12 in the selected active DBV712 group (250 µg) *versus* the placebo group,
- Description of the quality of life questionnaires (FAQLQ/FAIM) and change from baseline in FAQLQ/FAIM scores at Month 12 in the selected active DBV712 group (250 µg) *versus* the placebo group (for those countries where the translated and validated questionnaires are available and used).

Details of the assessment of each of the efficacy endpoints are provided in Section 6.1 and details of the corresponding statistical analysis are provided in Section 8.5.

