Peanut allergic children will be randomized based on the following key inclusion criteria: peanut allergy with the presence of peanut-specific IgE > 0.7K U/L and a SPT to peanut extract with the largest wheal diameter ≥ 6 mm and a positive DBPCFC with a peanut ED ≤ 300 mg of peanut protein.

A DBPCFC will be performed as it is the “gold standard” to diagnose and assess the food allergies (35). Since it carries a risk of inducing potentially severe allergic reactions, subjects will be appropriately selected and managed for the challenges, based on their clinical history and peanut-specific IgE test results.

The ED of peanut protein, that is the dose of peanut protein administered to subjects during the food challenge procedure, which triggers allergic reactions leading the challenge stop, is capped to 300 mg for the baseline food challenge, with the starting dose of 1 mg. Although the average amount of peanut consumed in an accidental exposure has not been accurately quantified, it is generally believed to be no more than 1 to 2 peanut kernels, or the equivalent of approximately 300 to 600 mg of peanut protein (24, 36, 37). Thus, this study will enroll subjects who will react at or below 300 mg peanut protein.

The second part of the study (Part B) is designed to assess the efficacy, the safety and tolerability of the selected dose of DBV712 patches, 100 µg or 250 µg, in this pediatric population (as from protocol v6.0, the selected dose for part B upon DSMB recommendation is 250 µg). The primary efficacy endpoint will rely on the difference *versus* placebo in the response to the peanut DBPCFC after 12-months of treatment.

The primary endpoint will be assessed at Month 12 based on positive results of previous clinical studies showing evidence of desensitization with peanut EPIT after 12 months of treatment.

An interim analysis will be conducted when 50 subjects from Part B will have reached 6 months of active treatment with the active dose selected in the Part A.

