### 8.9.2 Interim analysis of immunological activity

An analysis will be conducted when 50 subjects from Part B will have reached 6 months of active DBV712 treatment with the dose selected from the Part A (250  $\mu$ g). Immunological parameters (peanut-specific IgE and peanut-specific IgG4), SPT and main safety data will be presented.

A specific futility analysis will be conducted on the peanut-specific IgG4 measurements. The relative change from baseline [calculated as (Month 6 value – baseline value) / Baseline value] of the peanut-specific IgG4 levels in the selected active treatment group (250  $\mu$ g) will be numerically compared to the change in the placebo group. The median of the active group is expected to be greater than the placebo group median to evidence a treatment activity on the 1-3 year children's immune system.

In the situation where the median relative change from baseline of the peanut-specific IgG4 is equal or lower than the median relative change in the placebo group, the premature stop of the study for lack of evidence of therapeutic benefit will be considered. This unblinded data review will be conducted by the DSMB who will be responsible of issuing the recommendation to the sponsor.

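### Protocol 9.11 sets the IgG4 futility look when all Part B children reach 6 months, while six other places set the same look at 50 subjects; 9.11 is wrong as written and should be aligned

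*Protocol*

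**What the plan says.** Section 9.11 describes a DSMB meeting on the IgG4 futility analysis and the safety data, held "when all the subjects of the Part B will reach 6 months of treatment". The data are reviewed unblinded for "forming their recommendation on the continuation of the study".

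Six other places in the current protocol give a different trigger:

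- Synopsis, Study Part B, and section 3.1.2: "planned after the first 50 subjects from part B have received 6 months of active treatment" with the 250 µg dose, at Visit 8.
- Synopsis, interim futility analysis of the IgG4 response: "This analysis will be conducted when 50 subjects from Part B have reached 6 months of active treatment".
- Section 3.3.1.3: IgG4 change at Month 6 is named as "main criteria of the interim 6-month analysis of the first 50 subjects treated with the selected dose of DBV712".
- Section 3.4: "An interim analysis will be conducted when 50 subjects from Part B will have reached 6 months of active treatment".
- Section 8.9.2: "An analysis will be conducted when 50 subjects from Part B will have reached 6 months of active DBV712 treatment".

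Under 8.9.2, a premature stop is considered if the active median relative change in IgG4 is equal to or below the placebo median. The DSMB makes a recommendation to the sponsor. Section 3.4 treats the assessment as a stopping criterion, and section 9.13 lists a negative futility result among the grounds for ending the study. The SAP (section 5.10) gives no trigger and refers to a separate DSMB SAP and the DSMB charter.

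**The concern.** This is the only futility rule in the study, and it can lead to the trial being stopped. A futility look is useful if it comes early enough to limit how many children are enrolled and how long they are treated without benefit. The 50-subject triggers can do that. The 9.11 trigger waits until the last randomised child has had 6 months of patches.

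The two triggers also give different samples: 350 against 50 in total (7-fold), or against about 75 if 50 counts only children on active (350/75 = 4.7-fold). With both in force, the timing of the look is not fixed in advance, and either timing could be defended afterwards from the protocol. A smaller point is that the placebo number is never stated, although the rule compares two medians.

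**Working it through.** **1. One look or two?** Sections 8.9.2 and 9.11 agree on the marker (peanut-specific IgG4), the time on treatment (6 months), the body (DSMB), the data (unblinded) and the outcome (a recommendation on stopping or continuing). They differ only in who must have reached 6 months. No section describes a second futility look at full Part B enrolment. This is one look with two triggers.

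**2. The plan's own figure.** Inputs from the synopsis: rates of 40% and 10%, 2:1 allocation, Newcombe 95% lower bound of at least 15%, power of at least 90%. Exact binomial enumeration at 233 and 117 gives 90.9% power, and the smallest stable 2:1 total reaching 90% is 342. The planned 350 is reproduced.

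**3. How long can Part B accrual last?** The documents do not say, so accrual of A months is an assumption, taken as uniform. Section 9.12 plans about 30 months overall, with up to 6 weeks of screening, 12 months of treatment and up to 4 weeks of follow-up per child. Section 5.2 suspends recruitment after Part A until 3-month safety data are in.

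- Latest last randomisation: 30 − 12 − 0.9 = month 17.1. The 9.11 look then falls at 17.1 + 6 = about month 23.
- Longest Part B accrual: 17.1 − 1.4 (screening) − 3 (pause) = about 12.7 months, with no allowance for Part A's own accrual time.

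**4. State of the trial at the 9.11 look** (time A + 6, A at least 6, drop-out ignored).

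- Randomised: 350 of 350.
- Share past 12 months: (A − 6)/A.
- Share of planned treatment remaining: mean remaining time is 18/A months, so 18/(12A) = 1.5/A.

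**5. State at a 50-subject look.** With k children randomised first, t = A·k/350 + 6. If t is at most A, the share delivered is t²/(2A·12). If accrual has already ended, it is (t − A/2)/12. For A = 12 and k = 50: t = 7.7, delivered 7.714²/288 = 20.7%, remaining 79.3%.

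| Accrual (months) | Past 12 months at 9.11 look | Treatment left, 9.11 | Treatment left, 50 in total | Treatment left, 50 on active (about 75 randomised) |
|---|---|---|---|---|
| 6 | 0 (0%) | 25.0% | 67.9% | 64.3% |
| 9 | 117 (33%) | 16.7% | 75.4% | 70.9% |
| 12 | 175 (50%) | 12.5% | 79.3% | 74.5% |
| 12.7 | 185 (53%) | 11.8% | 80.0% | 75.0% |

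With 12-month accrual, 225 children (50 in total) or 250 (50 on active) would be randomised at the look, and none would have finished 12 months.

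**6. Which 50? Illustration only.** Let d be an assumed true shift, in SD units, on a log scale with roughly normal data. The chance that the active median is at or below the placebo median is Φ(−d/SE), with SE = 1.2533·√(1/n₁ + 1/n₀). SE is 0.374 at 33:17 and 0.307 at 50:25.

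| Shift d | 33:17 (50 in total) | 50:25 (50 on active) |
|---|---|---|
| 0.25 | 25% | 21% |
| 0.5 | 9% | 5% |
| 0.75 | 2% | 0.7% |
| 1.0 | 0.4% | 0.06% |

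The documents give no SD for IgG4 change, so no row is preferred.

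**The case against.** **It is a drafting slip in an administrative section.** Six places agree, including the statistical section, and the DSMB charter and DSMB SAP, which are not available here, may already fix the trigger. This is probably how the text arose. It does not cure it: 9.11 is where the protocol says when the DSMB meets, and section 9.10 requires the protocol to be followed exactly.

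**A reader might infer that a look under 9.11 has no futility value.** The documents do not support that. A stop could still spare the remaining treatment and the Month 12 challenge for every child not yet at 12 months: about 165 with accrual of 12.7 months (350 − 185), and all 350 with accrual of 6 months or less. If accrual took less than about 7 months, even the 50-subject look would follow full enrolment (A/7 + 6 exceeds A when A is below 7). The later look would also be less error-prone: at a 0.5 SD shift the false-flag chance at 233:117 is about 0.02%.

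**A reader might infer that most children, say two thirds, would have finished treatment.** That needs accrual of about 18 months ((18 − 6)/18 = 67%), which does not fit the 30-month plan with the pause after Part A.

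**A reader might infer that the meaning of 50 is wide open.** The wording already leans one way. Section 3.3.1.3 counts subjects treated with the selected dose, and the other five places speak of active treatment with that dose, which a placebo child cannot have received. What is missing is an explicit statement and a placebo number.

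**Conclusion.** The contradiction is real, stands in current text, and is not resolved by the protocol or the SAP. Section 9.11 is wrong as written. Following it would put the look after all 350 children are randomised, too late to limit enrolment and able to spare little treatment.

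The size rests on uniform accrual and no drop-out. Over 6 to 12.7 months the 9.11 look leaves about 25% to 12% of planned treatment undelivered, with 0% to about 53% of children already finished. A look at 50 in total leaves 68% to 79% for accrual of 6 to 12 months. The exact figures move with the assumed accrual; the ordering does not.

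The point goes no further than that. The rule is a non-binding numerical comparison on which the DSMB advises, so a flag is not a stop. It offers no route to an efficacy claim and leaves the primary alpha, power and sample size unchanged. The correction should be made because the rule can end the trial and the remedy is cheap.

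**What to change.** In 9.11, replace the trigger based on all Part B subjects with the 50-subject trigger of 8.9.2. Then use one definition in both synopsis passages (Study Part B and the interim futility analysis) and in 3.1.2, 3.3.1.3, 3.4, 8.9.2 and 9.11: the look takes place when the first 50 Part B children on DBV712 250 µg have completed Visit 8 (about 75 randomised at 2:1), and their IgG4 change is compared with that of the concurrently randomised placebo children. Align the DSMB charter and the DSMB SAP with that text. If a false-flag probability is quoted to support the choice, label it illustrative and show it over a range of assumed shifts.

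The cost is protocol wording and matching edits to the two DSMB documents. No extra children, visits or procedures are needed.
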